16.5 Electrocardiogram (ECG)

ECGs will be measured at screening Visit 1, Visit 3, Visit 6, and Visit 8/EOT, and graded as normal or abnormal. Abnormal findings or changes from baseline will be further classified as not clinically significant (NCS) or clinically significant (CS). In the event abnormal ECG results requires additional follow up, ECGs may be performed at unscheduled visits or at a study visit that an ECG is not required per protocol. ECG data performed outside of the protocol specified time points will be captured in the EDC on an "Unscheduled Visit" eCRF and mapped to the nearest scheduled visit as defined in [Section 9.3](#). ECG grades and shift from baseline will be summarized with counts and percentages for each visit for the Safety set. All clinically significant findings will be recorded as AEs in the eCRF and followed until resolution. Once resolved, the AE eCRF page(s) will be updated. A subject listing of the ECG results will also be produced.

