7.2.3 ELECTROCARDIOGRAM

Twelve-lead ECGs (I, II, III, aVR, aVL, aVF, V1 - V6) will be recorded using a computerized electrocardiograph. The ECGs will be recorded for a 10-second duration after the subjects have rested for at least 5 minutes in a supine position (see [Section 15.1, Schedule of Events Table](#), for time points). ECGs will be stored in the subject's medical records. ECGs may be repeated for quality reasons and the repeat ECG will

be used for analysis. Additional ECGs may be collected by the investigator for safety reasons. Abnormal findings will be reported as AEs (during the trial) or baseline conditions (at screening) in the eCRF.

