9.3 Visit Windows and Visit Mapping

The following table lists the scheduled visits and planned study day along with the corresponding visit window that will be used to map visits occurring outside of the scheduled times.

Scheduled Visit	Planned Study Day	Visit Window
Visit 1 / Screening	Day -7*	<= Day -1
Visit 2	Day 1	Day 1
Visit 3	Day 8	Day 2 to Day 11
Visit 4	Day 15	Day 12 to Day 18
Visit 5	Day 22	Day 19 to Day 25
Visit 6	Day 29	Day 26 to Day 32
Visit 7	Day 36	Day 33 to Day 39
Visit 8 / End of Treatment (EOT)	Day 43	Day 40 to Day 46
Visit 9 / Follow-Up (FU)	Day 50	Day 47 to Day 53
Visit 10 / FU	Day 57	Day 54 to Day 60
Phone / FU	Day 71	>=Day 61

* Visit 1/Screening of Fundus Photography/FA can be performed up to Day -14, per the protocol.

Summary tables will be presented by scheduled visit using the following algorithm. If there are multiple non-missing assessments within a visit window, then the visit closest to the scheduled visit will be used. If multiple visits are equidistant from the scheduled visit, then the scheduled visit and unscheduled visit

will be selected in that order. If multiple visits of the same type are equidistant from the scheduled window, then the earliest visit of that type will be selected.

Subject listings will include all visits.

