16.2 Slit-Lamp Biomicroscopy Examination

Slit-lamp biomicroscopy examinations will be conducted on both eyes at all scheduled visits. The slit-lamp findings will include examinations of the cornea, conjunctiva, anterior chamber, iris/pupil, lens and

eyelids. Anterior chamber will be graded as +, ++, +++ or none; the other parameters will be graded as normal or abnormal. Abnormal findings will be further classified as not clinically significant (NCS) or clinically significant (CS). All clinically significant values will be recorded as AEs in the eCRF and followed until resolution. Once resolved, the AE eCRF page(s) will be updated

Slit-lamp findings will be summarized by visit, for the study eye and fellow eye separately, using qualitative summary statistics (frequency counts and percentages). Percentages will be based on the number of subjects with non-missing values at a given visit.

A shift table will show changes from baseline Visit 2 (Day 1) to all observations at later study visits. The data for slit-lamp biomicroscopy examinations will be presented in a listing.

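### SAP 16.5 with the all-visit windows of SAP 9.3 puts unscheduled ECGs into by-visit rows where no ECG is planned, with no stated denominator and no any-time count of abnormal ECGs

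*SAP*

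**What the plan says.** SAP 16.5 opens with the planned schedule: "ECGs will be measured at screening Visit 1, Visit 3, Visit 6, and Visit 8/EOT, and graded as normal or abnormal". The schedules of events in the protocol (15.1) and the SAP (4.2) agree with it. SAP 16.5 then provides for follow-up of an abnormal result: "ECGs may be performed at unscheduled visits or at a study visit that an ECG is not required per protocol". Those ECGs are "mapped to the nearest scheduled visit as defined in" SAP 9.3. The tabulation rule is that "ECG grades and shift from baseline will be summarized with counts and percentages for each visit for the Safety set".

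SAP 9.3 gives a "visit window that will be used to map visits occurring outside of the scheduled times". There is one window per study visit and none specific to ECG. When a window holds several assessments, the one nearest the planned day goes into the summary table. A scheduled visit is preferred over an unscheduled one only when the two are equally distant. Listings show every visit.

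Protocol 7.2.3 is broader on why an extra ECG may be taken: "Additional ECGs may be collected by the investigator for safety reasons".

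SAP 16.5 names the Safety set but no percentage denominator. The slit-lamp section, SAP 16.2, does name one: "Percentages will be based on the number of subjects with non-missing values at a given visit". The titles of Tables 14.3.12.1 (overall results) and 14.3.12.2 (shift) do not say which visits appear.

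**The concern.** A by-visit safety table is read on the assumption that each row covers roughly the same subjects, so that a change between rows reflects a change in those subjects. At Visits 3, 6 and 8 that holds, apart from dropout. At a visit with no planned ECG, subjects are in the row because something prompted an ECG or because a planned ECG fell outside its window. A percentage from such a row, set beside one from a full row, can look like a spike or a recovery when only the group tested has changed.

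There is a second problem at the planned ECG visits. A recheck nearer the planned day displaces the scheduled ECG that prompted it, so the row can show normal for a subject whose scheduled ECG was abnormal. The ECG tables contain no count of subjects with an abnormal ECG at any time after baseline, so nothing in them recovers the displaced result.

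QTc prolongation is an event of special interest in both documents, so readers will look at the ECG tables.

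**Working it through.** The plan states no figure on this point, so there is nothing to reproduce. The check applies the SAP 9.3 windows to every day from Day 2 to Day 60 and then works through an illustrative row.

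**Step 1: where an off-schedule ECG lands.**

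| Visit | SAP 9.3 window | Days | ECG planned? |
|---|---|---|---|
| 3 | 2–11 | 10 | yes |
| 4 | 12–18 | 7 | no |
| 5 | 19–25 | 7 | no |
| 6 | 26–32 | 7 | yes |
| 7 | 33–39 | 7 | no |
| 8/EOT | 40–46 | 7 | yes |
| 9 | 47–53 | 7 | no |
| 10 | 54–60 | 7 | no |

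Total days: 10 + 7 × 7 = 59. Days in windows with no planned ECG: 5 × 7 = 35. So 35 of the 59 days, and 5 of the 8 post-baseline clinic visits, belong to visits without a planned ECG.

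**Step 2: who is in those rows.** Four routes lead there:
- a recheck after an abnormal ECG (SAP 16.5);
- an ECG taken for another safety reason (Protocol 7.2.3);
- a planned ECG done outside its window, for example a late Visit 3 ECG on Day 12, which falls in Visit 4;
- an early end-of-treatment ECG, for example on Day 20, which falls in Visit 5.

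The group is small and mainly selected, but it is not of one kind.

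**Step 3: what the percentage would show.** The counts are assumed. The 30 is the enrolment target, taken as the Safety set.

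Suppose 3 of 30 are abnormal at Visit 3: 3/30 = 10.0%. All three are rechecked in the Visit 4 window and 2 are still abnormal.
- Denominator, subjects tested: 2/3 = 66.7%.
- Denominator, Safety set: 2/30 = 6.7%.

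With one subject tested and abnormal, the two figures are 1/1 = 100% and 1/30 = 3.3%. If the Safety set were 25, the second figure would be 2/25 = 8.0% in the first example and 1/25 = 4.0% in the second.

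Neither choice estimates the Visit 4 rate of abnormal ECGs. The first covers only the selected subjects. The second treats the 27 untested subjects as not abnormal.

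**Step 4: displacement at a planned ECG visit.** Visit 6 is planned for Day 29. A scheduled ECG on Day 28 is abnormal and a recheck on Day 29 is normal. Distances from the planned day are |28 − 29| = 1 and |29 − 29| = 0. The recheck is closer, so Visit 6 is tabulated as normal. The preference for scheduled visits does not apply because there is no tie.

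**The case against.** Four arguments against the point have force.

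1. The phrase about each visit may mean each planned ECG visit, since SAP 16.5 opens by listing those. This is a fair reading. It leaves open, however, what becomes of an ECG mapped to Visit 4. SAP 9.3 says its algorithm serves the summary tables, while listings show everything, so a mapping instruction points towards the tables. Two programmers could build different tables from this text.

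2. A reader might infer that the off-schedule rows would consist only of subjects rechecked for an abnormal ECG. The documents do not support that, because safety ECGs, off-window planned ECGs and early end-of-treatment ECGs can land there too. What stands is that the group is not the full set of subjects due for an ECG.

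3. A reader might also infer a false spike from 10% to about 67%. That rests on assumed counts and on a denominator the SAP does not state. With the Safety set as denominator, the same counts give 6.7% and no spike. Counts are shown beside percentages in either case.

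4. The safety information is largely available elsewhere. SAP 16.5 sends clinically significant findings to the adverse event record, which is summarised once per subject. The QTc event has its own summary (Table 14.3.5) and listing (16.2.7.3), and would not be read from a table of normal and abnormal grades. Every ECG is in Listing 16.2.8.10. Safety variables carry no inferential testing (SAP 16), and the interim analysis in SAP 18 uses adverse event information. All of this stands. What is lost is the any-time count of ECGs graded abnormal, chiefly those judged not clinically significant, and a readable shift display.

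**Conclusion.** The point holds as a low-severity defect in two descriptive tables. Followed as written, SAP 16.5 and 9.3 produce rows at up to five visits where no ECG is planned, with percentages that are not rates and an unstated denominator. They also allow a normal recheck to replace an abnormal scheduled ECG. The ECG tables hold no any-time count to offset this.

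The window arithmetic (35 of 59 days, 5 of 8 visits) follows from the SAP. The 66.7% and 6.7% are illustrations from assumed counts, and the actual size depends on how many extra ECGs are taken, which the documents cannot tell us.

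It would be wrong to conclude that the trial cannot report ECG abnormality on treatment or that the QTc signal is hidden. The adverse event tables, the special-interest summary and the listings cover clinically significant findings and QTc. No conclusion of the trial depends on these two tables.

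**What to change.** Amend SAP 16.5 before database lock:

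- Limit the by-visit rows of Tables 14.3.12.1 and 14.3.12.2 to the planned post-baseline ECG visits (3, 6 and 8/EOT), against the baseline defined in SAP 9.2, which for ECG will usually be Visit 1.
- Assign scheduled ECGs to their nominal visit. Restricting the rows while keeping the SAP 9.3 windows would drop a planned ECG done off-window. Nominal assignment also stops a recheck from replacing the scheduled result.
- State how early end-of-treatment ECGs are shown.
- State the denominator of the by-visit percentages as subjects with a non-missing ECG at that visit.
- Add one row, worst post-baseline grade, using all scheduled and unscheduled ECGs, with treated subjects having at least one post-baseline ECG as denominator. State whether ECGs after the end of treatment count.
- Keep unscheduled ECGs in Listing 16.2.8.10 under their actual date.

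The cost is a few sentences and one extra row in each of two tables, with no new data and no change to trial procedures. The drawback is that the worst-grade row leans towards abnormality for subjects rechecked more often, since each recheck is another chance of an abnormal result. A footnote can say so.

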16.6 Vital Signs

Vital signs (blood pressure, pulse rate and respiration) and temperature will be summarized at all scheduled visits using descriptive statistics for the Safety set. Blood pressure includes systolic blood

pressure (SBP) and diastolic blood pressure (DBP). Change from baseline will also be summarized to each post-baseline visit.

A subject listing of the vital signs results will also be produced.

16.7 Physical Examination

A general physical examination including height (measured only at screening) and weight will be performed at screening Visit 1, Visit 2, Visit 4, Visit 6, Visit 8/EOT and Visit 10/FU.

Physical examination data will be listed to indicate whether the physical examination was conducted or not, but no tabular summaries will be produced.

17. Analysis of the Exploratory Endpoints

17.1 SD-OCT and Fundus Photography/Fluorescein Angiography

SD-OCT will be assessed at all scheduled study visits. The retinal layers and thickness will be visualized and measured by OCT and will be investigated by a trained person using only specified OCT equipment. Reported CST values will be exclusive of the sub-retinal pigment epithelial (RPE) layer fluid.

FP/FA will be conducted on the study eye at Screening (Day -7 to -2; up to 14 days prior to Visit 1 is also acceptable for FP/FA) and Visit 8/EOT (Day 43±1).

The following ophthalmic endpoints described below will be measured in an exploratory manner to investigate the extent, onset, and duration of action. Change from baseline in the study eye of the quantitative endpoints will be analyzed in a manner similar to the primary efficacy endpoint. Qualitative endpoints will be summarized for the study eye using counts and percentages for the Evaluable and PP sets. Subject listings will also be provided for these endpoints and will include collected data for the fellow eye.

- CST (μm) measured by SD-OCT, absolute and change from baseline
 - CST in the study eye will also be summarized for each scheduled visit using box plots.
- Presence and maximum height (microns) of IRF by SD-OCT over time, absolute and change from baseline
- Presence and maximum height (microns) of SRF by SD-OCT over time, absolute and change from baseline
- Presence and maximum height (microns) of PED by SD-OCT over time, absolute and change from baseline
 - Collected in EDC as RPE detachments and maximum height of the detachments are collected when present.

- Maximum height of PED in the study eye will also be summarized for each scheduled visit using box plots.
- Presence and size (number of disc areas) of CNV measured by SD-OCT and FP/FA, absolute and as change from baseline.
- Presence and size (number of disc areas) of CNV leakage as demonstrated by FP/FA, absolute and as change from baseline

The following ophthalmic endpoints will be captured in EDC as part of standard SD-OCT and FP/FA assessments. These endpoints will not be summarized (except for macular volume, which will be summarized for the study eye at scheduled visits using box plots) but will be presented in subject listings.

- Macular Volume (mm³) as measured by SD-OCT
- Presence of Intraretinal Cystoid Spaces as measured by SD-OCT
- Presence of Lesion in the CNV (including size of the lesion) as measured by FP/FA
- Presence of RPE atrophy as measured by FP/FA
- Presence of Hemorrhage in the PED (including area of the hemorrhage) as measured by FP/FA
- Presence of Disciform Scar/Retinal Fibrosis as measured by FP/FA

18. Interim Analyses

Continuous data monitoring will be performed. One interim analysis will be performed when two-thirds of all entered subjects have reached Day 15 (Visit 4). The interim analysis will include only a subset of the secondary endpoint (i.e., accumulated AE information).

Recruitment into the trial will be stopped if the interim analysis shows relevant safety problems with ALK4290. No formal futility analysis will be conducted.

19. Pharmacokinetic Analysis

A separate PK plan will be created to describe details pertinent to the analysis of collected PK data.

20. Biomarker Analysis

A separate biomarker plan will be created to describe details pertinent to the exploratory analysis of collected biomarker data.

21. Changes from Protocol-Stated Analyses

Not applicable.

22. References

Not applicable.

23. Revision History

Documentation of revision to the SAP will commence after approval of the Final version 1.0.

24. Tables

Tables that will be included in the topline delivery are shown in boldface font and the tables, listings, and figures for the interim analyses are italicized.

Table Number	Title	Set
14.1.1	Subject Disposition	All Subjects
14.1.2	Demographics and Baseline Characteristics	ITT Set
14.1.3.1	Ocular Medical History	ITT Set
14.1.3.2	Non-Ocular Medical History	ITT Set
14.1.4.1	Ocular Concomitant Medications	ITT Set
14.1.4.2	Non-Ocular Concomitant Medications	ITT Set
14.1.5	Compliance with Study Drug	Safety Set
14.1.6	Exposure to Study Drug	Safety Set
Primary and Exploratory Efficacy Analyses		
14.2.1.1	Summary of Study Eye BCVA Letter Score and Change from Baseline at Scheduled Visits	Evaluable Set
14.2.1.2	Summary of Study Eye BCVA Letter Score and Change from Baseline at Scheduled Visits	PP Set
14.2.1.3	Categorical Summary of Study Eye BCVA Letter Score Change from Baseline at Scheduled Visits	Evaluable Set
14.2.2.1	Summary of Study Eye Central Subfield Thickness (μm) and Change from Baseline as Measured by SD-OCT at Scheduled Visits	Evaluable Set
14.2.2.2	Summary of Study Eye Central Subfield Thickness (μm) and Change from Baseline as Measured by SD-OCT at Scheduled Visits	PP Set
14.2.3.1	Presence of Intraretinal Fluid as Measured by SD-OCT in the Study Eye at Scheduled Visits	Evaluable Set
14.2.3.2	Presence of Intraretinal Fluid as Measured by SD-OCT in the Study Eye at Scheduled Visits	PP Set
14.2.3.3	Summary of Maximum Height of Intraretinal Fluid (microns) and Change from Baseline as Measured by SD-OCT in the Study Eye at Scheduled Visits	Evaluable Set
14.2.3.4	Summary of Maximum Height of Intraretinal Fluid (microns) and Change from Baseline as Measured by SD-OCT in the Study Eye at Scheduled Visits	PP Set
14.2.4.1	Presence of Subretinal Fluid as Measured by SD-OCT in the Study Eye at Scheduled Visits	Evaluable Set
14.2.4.2	Presence of Subretinal Fluid as Measured by SD-OCT in the Study Eye at Scheduled Visits	PP Set

Table Number	Title	Set
14.2.4.3	Summary of Maximum Height of Subretinal Fluid (microns) and Change from Baseline as Measured by SD-OCT in the Study Eye at Scheduled Visits	Evaluable Set
14.2.4.4	Summary of Maximum Height of Subretinal Fluid (microns) and Change from Baseline as Measured by SD-OCT in the Study Eye at Scheduled Visits	PP Set
14.2.5.1	Presence of Pigment Epithelial Detachment as Measured by SD-OCT in the Study Eye at Scheduled Visits	Evaluable Set
14.2.5.2	Presence of Pigment Epithelial Detachment as Measured by SD-OCT in the Study Eye at Scheduled Visits	PP Set
14.2.5.3	Summary of Maximum Height of Pigment Epithelial Detachment (microns) as Measured by SD-OCT in the Study Eye at Scheduled Visits	Evaluable Set
14.2.5.4	Summary of Maximum Height of Pigment Epithelial Detachment (microns) as Measured by SD-OCT in the Study Eye at Scheduled Visits	PP Set
14.2.6.1	Presence of Choroidal Neovascularization as Demonstrated by Fluorescein Angiography in the Study Eye at Scheduled Visits	Evaluable Set
14.2.6.2	Presence of Choroidal Neovascularization as Demonstrated by Fluorescein Angiography in the Study Eye at Scheduled Visits	PP Set
14.2.6.3	Summary of Size of Neovascularization (Number of Disc Areas) and Change from Baseline as Demonstrated by Fluorescein Angiography in the Study Eye at Scheduled Visits	Evaluable Set
14.2.6.4	Summary of Size of Neovascularization (Number of Disc Areas) and Change from Baseline as Demonstrated by Fluorescein Angiography in the Study Eye at Scheduled Visits	PP Set
14.2.7.1	Presence of Leakage from Choroidal Neovascularization as Demonstrated by Fluorescein Angiography in the Study Eye at Scheduled Visits	Evaluable Set
14.2.7.2	Presence of Leakage from Choroidal Neovascularization as Demonstrated by Fluorescein Angiography in the Study Eye at Scheduled Visits	PP Set
14.2.7.3	Summary of Size of Leakage from Choroidal Neovascularization (Number of Disc Areas) and Change from Baseline as Demonstrated by Fluorescein Angiography in the Study Eye at Scheduled Visits	Evaluable Set
14.2.7.4	Summary of Size of Leakage from Choroidal Neovascularization (Number of Disc Areas) and Change from Baseline as Demonstrated by Fluorescein Angiography in the Study Eye at Scheduled Visits	PP Set
Safety Analyses		
14.3.1.1	Overall Summary of Treatment-Emergent Adverse Events	Safety Set
14.3.2.1	Summary of All Ocular Treatment-Emergent Adverse Events by System Organ Class and Preferred Term	Safety Set
14.3.2.2	Summary of All Non-Ocular Treatment-Emergent Adverse Events by System Organ Class and Preferred Term	Safety Set

Table Number	Title	Set
14.3.3.1	Summary of All Ocular Treatment-Emergent Adverse Events Suspected to be Related to Investigational Medicinal Product by System Organ Class and Preferred Term	Safety Set
14.3.3.2	Summary of All Non-Ocular Treatment-Emergent Adverse Events Suspected to be Related to Investigational Medicinal Product by System Organ Class and Preferred Term	Safety Set
14.3.4.1	Summary of All Ocular Serious Treatment-Emergent Adverse Events by System Organ Class and Preferred Term	Safety Set
14.3.4.2	Summary of All Non-Ocular Serious Treatment-Emergent Adverse Events by System Organ Class and Preferred Term	Safety Set
14.3.5	Summary of All Adverse Events of Special Interest by System Organ Class and Preferred Term	Safety Set
14.3.6.1	Summary of All Ocular Treatment-Emergent Adverse Events Leading to Subject Withdrawal by System Organ Class and Preferred Term	Safety Set
14.3.6.2	Summary of All Non-Ocular Treatment-Emergent Adverse Events Leading to Subject Withdrawal by System Organ Class and Preferred Term	Safety Set
14.3.7.1	Summary of Ocular Treatment-Emergent Adverse Events by Maximum Severity, System Organ Class and Preferred Term	Safety Set
14.3.7.2	Summary of Non-Ocular Treatment-Emergent Adverse Events by Maximum Severity, System Organ Class and Preferred Term	Safety Set
14.3.8.1	Summary of Slit Lamp Biomicroscopy	Safety Set
14.3.8.2.1	Shift in Overall Results of Slit Lamp Biomicroscopy	Safety Set
14.3.8.2.2	Shift in Slit Lamp Biomicroscopy Anterior and Vitreous Chamber	Safety Set
14.3.8.2.3	Shift in Slit Lamp Biomicroscopy Hypopyon and Retinal Tear and Detachment	Safety Set
14.3.8.2.4	Shift in Slit Lamp Biomicroscopy Lens Status	Safety Set
14.3.8.2.5	Shift in Slit Lamp Biomicroscopy Lens Opacity for Phakic Eyes	Safety Set
14.3.9	Summary of Intraocular Pressure	Safety Set
14.3.10.1.1	Summary of Clinical Laboratory Values - Biochemistry	Safety Set
14.3.10.1.2	Shift in Clinical Laboratory Values - Biochemistry	Safety Set
14.3.10.2.1	Summary of Clinical Laboratory Values - Coagulation	Safety Set
14.3.10.2.2	Shift in Clinical Laboratory Values - Coagulation	Safety Set
14.3.10.3.1	Summary of Clinical Laboratory Values - Hematology	Safety Set
14.3.10.3.2	Shift in Clinical Laboratory Values - Hematology	Safety Set
14.3.11	Summary of Vital Signs	Safety Set
14.3.12.1	Summary of Electrocardiogram Overall Results	Safety Set
14.3.12.2	Shift in Electrocardiogram Overall Results	Safety Set

25. Listings

Listing Number	Title	Set
16.2.1	Subject Disposition	ITT Set
16.2.2	Protocol Deviations	ITT Set

Listing Number	Title	Set
16.2.3.1	Inclusion and Exclusion Criteria	All Patients
16.2.3.2	Subjects Excluded from Analysis Sets	ITT Set
16.2.3.3	Informed Consent	ITT Set
16.2.4.1	Demographics	ITT Set
16.2.4.2	Ocular Medical History	ITT Set
16.2.4.3	Non-Ocular Medical History	ITT Set
16.2.4.4	Prior and Concomitant Ocular Medications	ITT Set
16.2.4.5	Prior and Concomitant Non-Ocular Medications	ITT Set
16.2.5.1	Study Drug Administration	ITT Set
16.2.6.1	Best Corrected Visual Acuity Scores (ETDRS)	ITT Set
16.2.6.2	Spectral Domain – Optical Coherence Tomography	ITT Set
16.2.6.3	Fundus Photography	ITT Set
16.2.6.4	Fluorescein Angiography	ITT Set
16.2.7.1	All Adverse Events	ITT Set
16.2.7.2	Serious Adverse Events	ITT Set
16.2.7.3	Adverse Events of Special Interest	ITT Set
16.2.7.4	Adverse Events Leading to Subject Withdrawal	ITT Set
16.2.7.5	Deaths	ITT Set
16.2.8.1	Slit-Lamp Biomicroscopy	ITT Set
16.2.8.2	Intraocular Pressure	ITT Set
16.2.8.3	Vital Signs	ITT Set
16.2.8.4	Physical Examination	ITT Set
16.2.8.5	Biochemistry	ITT Set
16.2.8.6	Hematology	ITT Set
16.2.8.7	Coagulation	ITT Set
16.2.8.8	Urine Analysis	ITT Set
16.2.8.9	Serology	ITT Set
16.2.8.10	Electrocardiogram	ITT Set

26. Figures

Figure Number	Title	Set
14.2.1	By-Visit Box Plot Summary of BCVA Letter Score in the Study Eye	Evaluable Set
14.2.2	By-Visit Box Plot Summary of Central Subfield Thickness (μm) in the Study Eye as Measured by SD-OCT	Evaluable Set
14.2.3	By-Visit Box Plot Summary of Macular Volume (mm^3) in the Study Eye as Measured by SD-OCT in the Study Eye	Evaluable Set
14.2.4	By-Visit Box Plot Summary of Maximum Height of Pigment Epithelial Detachment (microns) as Measured by SD-OCT in the Study Eye	Evaluable Set

27. Appendix 1

The following algorithms will be used to impute partial dates.

Assessment Type	Start Date	End Date
Medical History	
If only day is missing then impute day as the first of the month ('01').
 
If missing day and month then impute the first of the year ('01JAN').
	
If only day is missing then impute day as the last day of the month ('31' for months 01, 03, 05, 07, 08, 10, 12; '30' for months 04, 06, 09, 11; '29' for month 02 if a leap year; '28' for month 02 if not a leap year).
 
If missing day and month then impute the last of the year ('31DEC').

Prior and Concomitant Medications	
If only day is missing and the month and year are the same as the date of IMP initiation, then impute day as the day of IMP initiation.
 
If only day is missing and month and year are not the same as the date of IMP initiation, then impute the first day of the month ('01').
 
If missing day and month and the year is the same as the date of IMP initiation, then impute day and month as the day and month of IMP initiation.
 
If missing day and month and the year is not the same as the date of IMP initiation, then impute day and month as the first of the year ('01JAN').
	
If only day is missing then impute day as the last day of the month ('31' for months 01, 03, 05, 07, 08, 10, 12; '30' for months 04, 06, 09, 11; '29' for month 02 if a leap year; '28' for month 02 if not a leap year).
 
If missing day and month then impute the last of the year ('31DEC').

Adverse Events
	
Patial start dates for AEs will not be collected.
 
Completely missing start dates for AEs will be imputed as the first dose date unless the corresponding end date indicates the AE could have start earlier, in which case the missing date will be imputed as 01Jan of the same year as the end date.
	
Patial end dates for AEs will not be collected.
 
Completely missing end dates for AEs will not be imputed.

-----------------------	--	---
